## 6. DATA ANALYSIS PLAN

Hypothesis tests will be performed using a two-sided significance level (type I error) of  $\alpha$ =0.05. Aim 1 (Hypotheses 1 and 2) outcome will be evaluated using binominal regression models with adaptive elastic net penalty to examine the association between total sleep time and POD. Patient characteristics of interest (i.e. age, gender, baseline cognitive score, pain, depression symptom score, frailty index, Charlson comorbidity index) will be included into this regression model. Because missing data rarely occur entirely at random, we will assess associations between patient characteristics with respect to missing data. If patients with at least one missing outcome value are different from those with complete outcomes data, we will use multiple imputation to assign values to missing data risk factors and outcomes in regression modeling. Aim 2 (Hypothesis 1) Wilcoxon rank-sum tests with corrections for multiple comparisons will be used to assess differences for each analyte or transcript. In other exploratory analysis, we will assess differences in the EEG (PSG and intraoperative) dynamics of delirious and non-delirious patients. To assess statistical significance for the difference in EEG spectra at each frequency, we will compute the 99% confidence interval of the median difference between groups by using an empirical bootstrap approach. The null hypothesis will be rejected only if the confidence interval of the median difference at each frequency exceeds the significance threshold over a contiguous frequency range  $\geq$  2W. We will also characterize differences in sleep microstructure dynamics (i.e. spindle power, spindle rate, spindle peak frequencies, slow-delta phase- spindle amplitude modulation) between groups using algorithms developed in-house.

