## AIM 1: To use PSG and a validated sleep questionnaire to characterize sleep quality in POD patients Hypothesis 1.1. POD will be associated with significantly decreased pre-operative total sleep time

Hypothesis 1.2. POD will be associated with a pre-existing history of sleep disruption as measured by the Pittsburgh Sleep Quality Assessment (PSQI)

AIM 2: To use serum profiling to understand the association between POD and circadian disruption Hypothesis 2.1. POD will be associated with decreased am mRNA transcript levels of clock genes (Bmal1, Clock, Per1 and Per2).

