#### Treatment Assignment and Randomization: Not applicable.

#### 5. Study Design

Pre-operative Visit: We will obtain a written consent prior to conducting the Long-CAM, PSQI, Patient Health Questionnaire (PHQ-9), Trust in Physician Scale (TPS) and the abbreviated Montreal cognitive assessment. Next, we will place a portable PSG device at approximately 7 pm to record neurophysiological data using the Compumedics Portable PSG monitoring device. Due to clinical care concerns, patient acuity, patient unavailability and several other unforeseen factors, PSG may not be placed on all study subjects. A minimum of the following electrodes will be placed for sleep staging: Two central channels (C3 and C4), two electrooculogram channels to capture lateral eye movements, and two reference channels over the left and right mastoids.

Post-operative Day 0: PSG electrodes will be removed at approximately 6am. Additionally, we will obtain approximately 13ml of blood to be processed into mRNA to understand the association between peri-operative circadian cycle disruption of four circadian clock genes (Bmal1, Clock, Per1 and Per2) and POD. The PI will ensure that appropriate privacy and de-identification procedures are in place for the collection and storage of blood. All MGH ORs are equipped with a four-channel frontal EEG device (Sedline, Masimo, Irvine, CA). Thus, we will collect intraoperative routine EEG data that is recorded as part of routine anesthetic management. Due to clinical care concerns, patient acuity, Sedline electrode unavailability and several other unforeseen factors, blood and Sedline EEG data may not be obtained on all study subjects.

Post-operative Days 1-3: On post-operative day 1, we will obtain approximately 13ml of blood as a post-surgical measure of mRNA levels to understand the association between peri-operative circadian cycle disruption of four

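### For the primary question on total sleep time the plan names an adaptive elastic net, but no penalty exemption, tuning rule, 5% test or confidence interval

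*Combined protocol and SAP*

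**What the plan says.** Section 7 (Power Analysis) makes a difference in sleep duration between delirious and non-delirious patients the primary objective. Hypothesis 1.1 in Section 2 (Specific Aims) is worded as a significance claim: "POD will be associated with significantly decreased pre-operative total sleep time".

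Section 6 (Data Analysis Plan) opens with a general rule: "Hypothesis tests will be performed using a two-sided significance level (type I error) of" 0.05. For Aim 1, covering Hypotheses 1.1 and 1.2, it then gives one method: "binominal regression models with adaptive elastic net penalty to examine the association between total sleep time and POD". Seven patient characteristics join the model; the list ends "Charlson comorbidity index) will be included into this regression model". If patients with missing outcome values differ from those with complete outcomes, "we will use multiple imputation to assign values to missing data risk factors and outcomes in regression modeling".

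The same section is more explicit about inference elsewhere. For Aim 2, "Wilcoxon rank-sum tests with corrections for multiple comparisons will be used to assess differences for each analyte or transcript". For the exploratory EEG spectra it gives a decision rule: "The null hypothesis will be rejected only if the confidence interval of the median difference at each frequency exceeds the significance threshold" over a stated frequency width.

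**The concern.** The model family, outcome, covariates, sidedness and significance level are all prespecified. The statistic to which the level applies is not. An adaptive elastic net does not by default return a standard error, p-value or interval, and neither reading of the penalty fills the gap:

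- **TST penalised.** The coefficient is pulled toward zero, and being selected is not a 5% decision.
- **TST exempt.** It stays in the model whatever the data show, so a test must still be named.

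Imputation adds to the problem. Rubin's rules combine a within-imputation variance with the between-imputation variance, and the plan names no source for the former.

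At stake is the rule that decides the primary hypothesis. As written, the tuning criterion, or a switch to a refit, could be settled after the data are seen, and the estimate and the power depend on that choice.

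**Working it through.** **1. The plan's own figure (Section 7).** Inputs: 60-minute difference (360 versus 300), SD 60, alpha 0.05, power 0.90, 13 versus 78 (ratio 6).

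- Smaller group: n = (1 + 1/6) × (1.960 + 1.282)² × (60/60)² = 12.3, so 13; the larger group is 6 × 13 = 78.
- Noncentrality: 60 / (60 × √(1/13 + 1/78)) = 1 / 0.2996 = 3.34. Power is 0.916 (normal) or 0.910 (noncentral t, 89 df).

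The figure reproduces as a two-sided, unpenalised, unadjusted comparison of two means. Section 6 names no such comparison for TST.

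**2. True coefficient on the plan's scale.** With normal TST and a common SD, the logistic slope is the mean difference over the variance: -60/60² per minute, or -1.00 per 60 minutes. The model has TST plus seven covariates, so 13/8 = 1.6 delirium cases per term.

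**3. TST penalised.** The documents give no settings, so they were varied over 27 implementations: mixing 0.2, 0.5 and 0.8, crossed with nine set-ups differing in initial weights, weight exponent, which penalty carries the weights, and number and stratification of folds. Each used 13 versus 78, seven independent covariates, and 1,000 data sets per scenario (Monte Carlo SE at most about 1.5 points).

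| | Minimum-CV | One-SE rule |
|---|---|---|
| Mean coefficient per 60 min (true -1.00) | -0.58 to -0.93 | -0.13 to -0.32 |
| TST kept, 60-min difference | 92–99% | 61–83% |
| TST selected, no difference | 14–39% | 5–8% |

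Two further simulations agree in direction:

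- One (1,000 runs, ridge-based weights, mixing 0.5, 5 folds) selected TST under the null in 25.7% and 4.9%, and kept it under the effect in 96.6% and 74.2%. Its minimum-CV mean was -0.68 per pooled-sample SD. That SD is 60 × √(1 + (1/7)(6/7)) = 63.6 minutes, so the mean is about -0.65 per 60 minutes.
- The other (240 runs) gave mean coefficients of about -0.82 and -0.35.

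**4. TST exempt.** TST is kept in 100% of runs with or without an effect, with mean coefficient -1.06 to -1.10. Retention then carries no information.

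**5. TST tested at 0.05 in an unpenalised refit after selection** (ridge-based weights, 5 stratified folds, three mixing values, 1,000 runs each).

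- Null rejection: 4.3–7.6% (minimum-CV) and 1.8–3.1% (one-SE), although selection in those runs was 17–25% and 2–4%. With TST exempt it was 6.5–7.8%.
- Power at 60 minutes over the refit checks: about 0.90–0.93 (minimum-CV) against 0.72–0.82 (one-SE).

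**6. One candidate test: Firth logistic regression with all eight terms** (4,000 runs per scenario, independent covariates). Likelihood ratio: null rejection 4.6%, power 0.875. Wald: 3.9% and 0.856. A separate run of 2,000 gave 5.7% and 0.87 for the likelihood-ratio test.

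**The case against.** The strongest reply is that Section 6 announces 0.05 hypothesis tests at the outset, so testing a coefficient is at least as natural a reading as treating selection as the test. On that reading the error rate is not badly inflated (step 5). This stands. A reader might infer from the 14–39% row that the plan carries a false-positive rate of that size. The documents do not support that, because nowhere do they say that selection means rejection. What remains is that the refit is not in the plan either, and its power still depends on an unstated tuning rule.

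A second reply is that Section 6 is brief throughout and Section 10 describes a physiological study rather than a clinical trial. This is partly right. It would be wrong to say that inferential detail is missing only for the primary objective: the Aim 2 multiplicity correction is unnamed, and the sleep microstructure comparisons have no test. Fold counts alone would be a minor omission. The absence of any test or interval for the primary question is not.

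Third, penalising is sensible with about 13 events and eight terms, and a logistic scale is a legitimate choice. Both points are accepted, and neither is the fault here. The sample size is not wrong either; 13 versus 78 reproduces.

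Finally, making Firth regression the primary analysis is a preference among valid methods. This is also accepted: it is one option.

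**Conclusion.** The point holds as a gap in prespecification that has consequences for the estimate. Section 6 sets a level for the primary question but provides nothing to which it can be applied. If all terms are penalised, the TST coefficient is reduced to about -0.6 to -0.9 (minimum-CV) or -0.1 to -0.4 (one-SE) against a true -1.00.

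If selection were read as significance, the null rate would be 14–39% with minimum-CV tuning and roughly 2–8% with the one-SE rule in the runs above. If a refit is tested, it is roughly 2–8% overall.

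That no test is stated follows from the text alone. The simulated sizes rest on assumed settings: exactly 13 versus 78, normal TST, independent covariates and complete sleep recording. They show sensitivity to unstated choices, not the plan's actual operating characteristics. This should be fixed before the data are seen.

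**What to change.** State in Section 6, before the data are seen:

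- **One confirmatory analysis of Hypothesis 1.1.** TST (per 60 minutes) is unpenalised by the elastic net and always retained, alongside the seven listed characteristics, with a named two-sided 0.05 test and a 95% interval. Firth logistic regression with a penalised likelihood-ratio test and profile interval is suitable. Another valid prespecified method for an unpenalised TST term would also do.
- **Pooling.** If the plan's imputation trigger is met, say how estimates and standard errors are combined, for example a Wald test and interval by Rubin's rules. The imputed analysis was not simulated here.
- **Hypothesis 1.2.** Treat the Pittsburgh index the same way, in its own model.
- **The adaptive elastic net.** Keep it for the covariates or as an exploratory analysis, with mixing parameter, weights, folds and tuning rule stated.
- **Section 7.** Describe the 0.90 as the power of an unadjusted two-mean comparison (0.910 at 13 versus 78).

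The cost is a few sentences and standard software, with no new patients or data. Power is about 0.86–0.88 instead of 0.91 if covariates are unrelated to TST and POD and all 91 patients have a sleep recording. It will differ if covariates are related to both. It will be lower if recordings are missing, which Section 5 allows for ("PSG may not be placed on all study subjects"). The same is true of any adjusted analysis, including the plan's own.

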### 3. Subject Selection

**Primary inclusion criteria for patients:** 1) age  $\geq$  60; 2) inpatient and scheduled for surgical procedure at MGH. **Primary exclusion criteria for patients:** 1) blindness, deafness or the inability to speak English; 2) inability to provide informed consent.

Primary objective drop for patients: 1) post-operative intubation >24 hours.

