### 4. Subject Enrollment

**Recruitment:** This study will be performed at the Massachusetts General Hospital in Boston, MA. We will enroll 100 male and female patients into the study. Cardiac surgical patients and orthopedic trauma patients represent the primary surgical patients that are admitted to the hospital prior to their surgical procedures. Thus, we will screen cardiac and orthopedic surgical schedules to identify potential eligible subjects. We will engage members of the patient's clinical care team to ask the patient if he/she is willing to have a study team member approach him/her to discuss a research study. This initial care patient contact will be performed by cardiac or orthopedic clinical staff (M.D., P.A, N.P, R.N), cardiac or orthopedic anesthesia care providers (M.D., C.R.N.A, S.R.N.A), or hospital geriatric clinicians (M.D., P.A, or N.P). Study team members will only approach patients that are interested in learning more about the study. They will explain the details of the study and provide a flyer summarizing study procedures to the patient. Formal written consent will be obtained prior to any study related procedures.

**Retention**: All subjects who provide written consent but later decline participation in the study will not be subject to any study-related follow-up.

**Remuneration:** There will be no monetary remuneration for this study.

**Procedure for informed consent:** Members of the patient's clinical care team will briefly introduce the study to the patient. Study team members will only approach patients that are interested in learning more about the study. Study team members will explain the details of study and provide a flyer summarizing study procedures to the patient. If the study team member is a non-physician (i.e. clinical research coordinator), he/she will explicitly offer the patient an opportunity to speak to physician investigators. The study team member will review and discuss the details of the research study with the patient using the informed consent document as a guide. The discussion will include all the required elements of informed consent. A formal written consent will be obtained only after all questions and concerns have been addressed.

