circadian clock genes (Bmal1, Clock, Per1 and Per2) and POD. Delirium assessments may be conducted twice daily (AM and PM with at least 6 hours between tests) beginning on postoperative day 1 using the Long Confusion Assessment Method (CAM). PHQ-9 will be assessed on POD 3 only. Subjects who elect to withdraw from the study during their hospital stay will be re-approached by the study team within 8-24 hours of study withdrawal. The study team member will elicit the reason for study discontinuation and confirm the withdrawal decision. This visit serves to ensure that the withdrawal decision was made during an informed and non-delirious cognitive state. In the event that a subject finds it difficult to complete an assessment (i.e. pain, clinical intervention), only the long-CAM domains necessary to dispel the presence of delirium will be assessed (i.e. acute onset, inattention, disorganized thinking and altered level of consciousness). Subjects who cannot complete this shortened assessment will be re-approached several hours later. Long-CAM assessments for subjects who are reintubated for clinical care or for further surgical management will be considered missing data.

Post-operative Day 30: PHQ-9 and the Pain Interference 8a (PROMIS SF v1.0) questionnaires will be administered over the phone. Subjects' infection rates will also be tracked postoperatively.

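### The Aim 1 model adjusts for seven covariates but not for surgery type, although the cohort mixes cardiac and orthopedic patients

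*Combined protocol and SAP*

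**What the plan says.** Section 4 explains who will be in the cohort: "Cardiac surgical patients and orthopedic trauma patients represent the primary surgical patients that are admitted to the hospital prior to their surgical procedures". It continues: "we will screen cardiac and orthopedic surgical schedules to identify potential eligible subjects". Section 3 sets no limit by type of operation; a patient must be "inpatient and scheduled for surgical procedure at MGH". The entry just before Section 5 confirms that this is an observational study: "Treatment Assignment and Randomization: Not applicable".

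Section 6 analyzes Aim 1 with "binominal regression models with adaptive elastic net penalty to examine the association between total sleep time and POD". It chooses to adjust and names the covariates: "Patient characteristics of interest (i.e. age, gender, baseline cognitive score, pain, depression symptom score, frailty index, Charlson comorbidity index". That makes seven. Surgery type or service is not one of them, and no section stratifies, adjusts or runs a sensitivity analysis by service. The power calculation in Section 7 is an unadjusted two-group comparison of sleep time.

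**The concern.** Hypothesis 1.1 and the primary objective in Section 7 are both about an association between POD and pre-operative sleep time. In a non-randomized cohort drawn from two services, service is an obvious candidate confounder. It is fixed before sleep is recorded and may be related both to how a patient sleeps before surgery and to the risk of delirium.

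The association is distorted only if sleep time and POD risk both differ by service after allowing for the seven covariates. If the higher-risk service sleeps less, the omission adds to the association; if it sleeps more, the omission masks a real one. The protocol's own literature summary in Section 1 classifies earlier studies by type of surgery, with 9 of 12 in a single specialty (5 orthopedic, 4 cardiac). That shows surgery type is treated as a relevant descriptor. It does not show that sleep or POD differs by service here.

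**Working it through.** **The plan's own figure.** Inputs from Section 7: SD 60 min, difference 60 min, two-sided alpha 0.05, power 0.90, groups of 13 and 78 (ratio r = 6). The number with POD is (1 + 1/r) × (1.960 + 1.282)² × (60/60)² = 12.26, rounded up to 13, and 6 × 13 = 78. The total is 91. Allowing for 10% dropout, 91/0.9 = 101.1, so 102 against the 100 stated. The sample size reproduces; noncentral t power is 0.910.

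**Assumed inputs.** The documents give nothing by service. Assumed throughout: a 50:50 mix, overall POD 15%, overall SD 60 min, and no sleep-POD association within either service. POD risk is 10% v 20%, or 5% v 25% as an extreme. The higher-risk service sleeps 30 or 60 min less.

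**Before any adjustment.** Spurious difference = (share of the high-risk service among POD patients − its share among the rest) × sleep gap.
- 10% v 20%: 0.5 × 0.20/0.15 − 0.5 × 0.80/0.85 = 0.667 − 0.471 = 0.196. This gives 5.9 min at a 30-min gap and 11.8 min at 60; a 13 v 78 t test rejects in 6.2% and 9.9% of studies.
- 5% v 25%: 0.833 − 0.441 = 0.392. This gives 23.5 min at a 60-min gap and 25.4% rejection.

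**After the seven covariates.** Suppose they explain 25% or 50% of the variance in service. Simulation used a linear model of sleep on POD at n = 91 (6,000 studies per setting; Monte Carlo standard error about √(0.05 × 0.95/6,000) = 0.3 points). Odds ratios come from a large-sample logistic model of POD on sleep, the direction the plan uses. Each cell shows 25% / 50% explained.

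| POD risk | Sleep gap | Spurious difference (min) | Type I error | Spurious OR per 60 min less sleep |
|---|---|---|---|---|
| 10% v 20% | 30 min | 4.6 / 2.5 | 5.9% / 4.9% | 1.08 / 1.06 |
| 10% v 20% | 60 min | 9.1 / 5.4 | 7.7% / 5.8% | 1.17 / 1.13 |
| 5% v 25% | 60 min | 17.8 / 12.3 | 16.2% / 10.6% | 1.38 / 1.27 |

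With a surgery term, the 10% v 20% difference is −0.5 to 0.2 min and type I error 4.9% to 5.0%. At 5% v 25% type I error is 5.2%. The odds ratios become 0.99 to 1.01. For scale, the 60-min design effect corresponds to exp(60 × 60/60²) = 2.7 (normal sleep times, equal SDs).

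Section 5 warns that "PSG may not be placed on all study subjects". With sleep data on only 60 to 75 patients, the 10% v 20% figures stay at about 3 to 9 min and 5% to 7%.

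**Binomial model at n = 91.** Firth logistic type I error, without v with the term:
- 10% v 20%, 30-min gap, 25% explained: 5.1% v 4.3%.
- 10% v 20%, 60-min gap, 25% explained: 6.1% v 4.6%.
- 10% v 20%, 60-min gap, 50% explained: 4.3% v 3.2%.
- 5% v 25%, 60-min gap, 25% explained: 13.5% v 3.4%.

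**Adaptive elastic net.** Tuning is not given, so mixing 0.5, a ridge start and 5-fold cross-validation were assumed, with 25% explained and 600 null datasets (standard error about 2 points). A null sleep term is retained, without v with an unpenalized surgery term, in 20% v 20% (10% v 20%, 30 min), 25% v 17% (10% v 20%, 60 min) and 44% v 17% (5% v 25%, 60 min). If the surgery term is itself penalized, it is dropped in 52% to 55% of the 10% v 20% datasets.

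**Masking.** With a true difference of 60 min, POD 10% v 20% and the sleep gap reversed, the estimate without the term is 51 to 57 min and power 79% to 86%, against 88% to 94% with it.

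**The case against.** The strongest reply is that no problem has been shown. Every input by service is assumed, and a 60-min gap is a full SD and equal to the whole design effect. At a 30-min gap the distortion is close to nil: 2.5 to 4.6 min, Firth type I error 5.1%, and no change in elastic-net retention. This stands, and it is why the point is graded as a modest bias rather than an error-rate problem.

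The seven covariates may also stand in for service better than assumed; if they explained 70% of it, the spurious difference would be 1 to 4 min. That is fair, but nothing in the documents supports any particular share.

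Part of the masking gain is precision, not bias removal. Holding overall SD at 60 with a 60-min gap leaves a within-service SD of √(60² − 30²) = 52 min. This stands: the 88% to 94% should not be read as recovered bias alone. The estimates of 51 to 57 min are the cleaner evidence.

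The covariate list may be open. Section 5 uses the same abbreviation loosely for examples: "In the event that a subject finds it difficult to complete an assessment (i.e. pain, clinical intervention". If so, surgery type is unspecified rather than excluded, and the choice would be made after the data are seen.

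Finally, the larger weaknesses are about 13 events and selection under the penalty. That is true, and the 17% to 20% retention of a null sleep term that remains with the surgery term shows it. It does not argue against one forced binary term.

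**Conclusion.** The concern holds as a cheap improvement that should be made. Surgery type is absent from the named covariates in a non-randomized cohort recruited from two services, and no other part of the plan handles it. Under POD 10% v 20%, a 30 to 60 min sleep gap and covariates explaining 25% to 50% of service, the omission produces about 3 to 9 min of spurious difference (odds ratio 1.06 to 1.17 against 2.7) and type I error of 5% to 8% in the linear approximation, or 4% to 6% with Firth logistic regression. Only the extreme case reaches 12 to 18 min and 11% to 16%. Confidence is medium, because the size rests wholly on assumed service-level inputs; the omission itself does not.

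**What to change.** In Section 6, pre-specify one binary surgery-type term (cardiac v non-cardiac) in the Aim 1 model, exempt from elastic-net selection. State a fallback: a ridge-only penalty on that term if one service has no POD case. Report within-service sleep differences as descriptive only. If the team prefers not to add the term, give the reason and report the sleep estimate with and without it.

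No new data are needed, since service is known from the screening schedule. The costs are:
- **Events per term:** 13/8 = 1.6 falls to 13/9 = 1.4. With only 60 recordings (0.15 × 60 = 9 events), 9/8 = 1.1 falls to 9/9 = 1.0.
- **Power for 60 min at n = 91 (linear model, seven covariates):** 0.875–0.879 falls to 0.866–0.875 at POD 10% v 20%, and 0.866–0.868 falls to 0.843 at 5% v 25%. The loss is about 3 points at n = 60 and 5% v 25%.
- **Chance of no POD case in the low-risk service:** at n = 91, 0.90^45.5 = 1% or 0.95^45.5 = 10%; at n = 60, 0.90^30 = 4% or 0.95^30 = 22%. The fallback therefore matters most where confounding is strongest.

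The change does not cure the sparse model or selection under the penalty.

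### Does the loosely worded trigger for multiple imputation in Aim 1 need to be pinned down before the data are seen?

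*Combined protocol and SAP*

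**What the plan says.** Section 6 (Data Analysis Plan) opens with a two-sided 0.05 level for hypothesis tests. It then specifies a binomial regression with an adaptive elastic net penalty relating total sleep time to post-operative delirium (POD). The covariates are listed: "Patient characteristics of interest (i.e. age, gender, baseline cognitive score, pain, depression symptom score, frailty index, Charlson comorbidity index".

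On missing data, the section first promises a descriptive step: "we will assess associations between patient characteristics with respect to missing data". The condition follows: "If patients with at least one missing outcome value are different from those with complete outcomes data, we will use multiple imputation". Once triggered, imputation is used "to assign values to missing data risk factors and outcomes in regression modeling", so it covers predictors as well as the response.

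Section 5 (Study Design) shows that both sides of the model may have gaps. For sleep recording: "Due to clinical care concerns, patient acuity, patient unavailability and several other unforeseen factors, PSG may not be placed on all study subjects". For delirium: "Delirium assessments may be conducted twice daily (AM and PM with at least 6 hours between tests) beginning on postoperative day 1", and "Long-CAM assessments for subjects who are reintubated for clinical care or for further surgical management will be considered missing data". The same paragraph provides a shortened assessment and a return visit some hours later for patients who cannot complete the full one.

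Section 7 (Power Analysis) frames the primary objective as a difference in sleep duration between patients with and without delirium.

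**The concern.** The sentence reads like an objective gate, yet three of its parts are open.

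- **Outcome.** The regression makes POD the response, while Section 7 compares sleep duration between groups. On the first reading, a patient with delirium assessments but no sleep recording does not count toward the trigger, although the plan expects such patients. Also, up to six delirium assessments are possible per patient (two a day for three days). Read literally, one missed assessment puts a patient in the missing group even if another assessment already shows delirium.
- **Different.** No test, threshold or multiplicity rule is named for the seven characteristics.
- **Otherwise.** No analysis is named for the case where no difference is found.

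At stake would be the primary result. Complete-case and imputed analyses of the same data sometimes fall on opposite sides of p = 0.05. A choice between them made after seeing both could inflate the type I error.

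**Working it through.** **1. The plan's own figure.** Inputs from Section 7: difference 60 minutes, SD 60 minutes, two-sided alpha 0.05, power 0.90, groups of 13 and 78 (1:6).

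- Smaller group: (1 + 1/6) × (1.960 + 1.282)² × (60/60)² = 1.167 × 10.51 = 12.3, so 13. The larger group is 6 × 13 = 78.
- Power at 13 and 78: the standardised effect is 1/√(1/13 + 1/78) = 3.34, giving 0.916 by the normal approximation and 0.910 by the noncentral t.
- 100 recruited less 10% leaves 90.

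The sample size reproduces and is not in dispute.

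**2. How often the trigger fires by chance.** Take seven characteristics, data missing completely at random, and the 0.05 level from the opening of Section 6.

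- Any of seven below 0.05, independent: 1 − 0.95⁷ = 0.302. With correlations of 0.3 to 0.5 between characteristics, simulation gives 0.23–0.28.
- Bonferroni: 1 − (1 − 0.05/7)⁷ = 0.049.

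Much higher rates (82% to over 99%) appear only with cut-offs of 0.25 or 0.1 on a standardised difference. The documents contain no such cut-off. With 9 of 90 missing, the standard error of a standardised difference is √(1/9 + 1/81) = 0.35, so those cut-offs would mostly fire on noise. The range supported by the text is about 5% to 30%.

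**3. What following the rule does to the test.** Simulation inputs: 13 against 77 patients; sleep time missing completely at random in 10, 20 or 30% (assumed, since the documents give no rate). Impute if any of the seven characteristics has p < 0.05; otherwise use a complete-case t-test.

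| Procedure | Type I error |
|---|---|
| Complete-case alone or imputation alone | 0.047–0.051 |
| Rule as written, any of seven | 0.046–0.054 |
| Run both and keep the better p-value | 0.053–0.064 |

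Power under the rule stayed within about 1 point of either analysis alone. The rule does not inflate error because the trigger never looks at the sleep–POD association.

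**4. How often the two analyses disagree at p < 0.05.** With a true 60-minute difference, at 10, 20 and 30% missing:

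- t-test: 2–3%, 4–6% and 6–9%.
- Unpenalised logistic regression: 3%, 5–6% and 8–11%.
- With no true difference (t-test): 1–3% overall.

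**5. Missed delirium assessments.** If each of six assessments is missed independently with probability q, the share of patients with at least one missed is 1 − (1 − q)⁶: 11%, 26% and 47% at q = 2, 5 and 10%. Both the rates and the independence are assumptions. The cause that Section 5 names, reintubation, would cluster within patients. Under complete clustering, 10% of assessments missed means 10% of patients, not 47%. The central hypothesis in Section 1 concerns incidence of POD, a patient-level status, so a patient with one positive assessment already has a known outcome.

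**The case for a change.** The strongest case for a change is that the sentence fixes very little and the repair is cheap: name one analysis as primary and the other as sensitivity, in two or three sentences, with no extra patients or data. The rule will probably be needed, because Section 5 itself anticipates missing sleep recordings and missing delirium assessments. If POD is the outcome, missing sleep time, the main exposure, cannot start imputation by itself, and the plan does not say how it is then handled. With a real 0.5 SD difference in one characteristic and 9 patients missing, the trigger fires in 13% of studies under Bonferroni and 47% under any of seven, so the unstated criterion matters.

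The factual part stands: the test, the fallback analysis and the treatment of partly missing assessments are not stated. The inference to harm does not.

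- POD is the response in the binomial model, and the imputation sentence separates risk factors from outcomes, so the meaning of 'outcome' is largely settled by the text.
- Complete-case analysis is the obvious default when imputation is not triggered.
- Both analyses held their nominal level in the settings simulated, and neither is clearly better as primary. Complete-case avoids pooling penalised fits with 13 or fewer delirium cases. Imputation has more appeal if absence of a recording follows patient acuity. Choosing between them is a trade-off, not the correction of an error.

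**Conclusion.** No change is needed. Section 6 leaves detail unstated, but an analyst would fill it sensibly: POD as the outcome, tests at 0.05, complete-case analysis if no difference is found, and delirium judged per patient. Under that reading the trigger fires by chance in about 5% to 30% of studies, type I error stays at 0.046–0.054 (simulated for the any-of-seven version), and power moves by about 1 point at most. The worst case, running both analyses and keeping the better one, adds at most 0.064 − 0.05 = 1.4 percentage points, and the plan does not propose doing that.

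This rests on assumed missing rates of 10–30%, data missing completely at random, and t-tests in place of the adaptive elastic net. The type I error and power results have not been shown for the penalised regression or for missingness that depends on acuity. A sentence naming the main and the sensitivity analysis would be a courtesy to readers, but the validity of the primary comparison does not depend on it.
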